Following enrolment in the study, deferred informed consent will be sought from the patient within a reasonable timeframe following clinical assessment/treatment (within 72 hours for first contact). Information will be provided and consent sought for the continuation in the study, and for continued use of data obtained. If the patient lacks capacity, a consultee will be consulted as soon as possible and given information about the study. The consultee will advise as to whether the person should take part in the study, and what the person's wishes and feelings about taking part in the project would be if they had capacity to decide (Mental Capacity Act s32) [1]. The consultee does not give consent themselves. The choice of who acts as consultee is important. A consultee should be someone who is close to the patient, is trusted by them, and knows them well enough to advise what their wishes and preferences about participating would be [31]. Informed consent will also be sought from the patient themselves as soon as possible following any regaining of capacity. If the consultee so advises, the participant must not take part and, if already taking part, must be withdrawn. If the person who lacks capacity indicates (in any way) that they wish to be withdrawn from the study, they

must be withdrawn without delay without having to give reasons, if they don't want to and without prejudicing their further treatment. In cases where the participant dies following the intervention, we will continue to use their data. In instances where the original copy of the consent form cannot be obtained, for example due to restrictions on paperwork leaving the bedspace because of confirmed or suspected COVID-19 or use of a continuous positive airway pressure (CPAP) machine, local NHS Trust/Health Board policies will be followed such as taking a photograph of the signed consent form and sending it to the research delivery staff for printing out and filing in the Site File.

The use of anonymous data from deceased persons is lawful, and consent is not legally required from the person before they die or from a nominated representative however a letter informing them of the participants inclusion in the study will be sent along with contact details of the study team if they have further questions. A flowchart for the consent process can be seen in Figure 2.

Figure 2: Participant Consent Flowchart.

Footnotes

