10.1 Adherence

Adherence to the algorithm will be recorded on the CRF and will capture instances where the treating clinician overrules the algorithm if they feel it is appropriate to do so. The ultimate responsibility for clinical care of the patient lies with the treating clinician therefore the cut – off boundaries for initiation times of antibiotics are not mandatory but are recommended guidance to aid clinical decision making. The aim of the trial is to assess whether the use of PCT can improve decision making about which patients receive antibiotics and in what time period. Deviations from the algorithm will not be recorded as protocol violations.

11 Trial procedures

All participants will be prospectively enrolled in the trial from the date of randomisation and will be assessed up to and including day 28 or until they are discharged from clinical care (for those enrolled in the last three months of the trial). Assessments include antibiotic initiation, antibiotic use, adverse events, ICU usage (details of admission to ICU), unscheduled readmissions (ICU re-admissions, re-admissions post discharge), mortality (death for any reason in the 28 days following randomisation), discharge before Day 28, and serious adverse drug reactions (ADRs) to the antibiotic. All clinical management decisions will be recorded at all time points.

At Day 28 and Day 90 there will be a follow-up via telephone or electronically (email/text) about the healthcare utilisation and quality of life of the participant. If unsuccessful a questionnaire booklet will be posted to the participant for them to complete and return with a pre-paid envelope.

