11.1 Assessments

Outcome data will be recorded daily by the research nurse for all recruited participants (up to and including Day 28, or until discharge). Patient reported outcome data (health-related quality of life and resource use questionnaires) will be recorded at day 28 and day 90 (with the exception of those recruited within the last 3 months of the study).

Research nurses will review observation and medication charts, and medical notes for all recruited participants to collect the data described in Table 1 below:

Table 1: Outcome data collection

Outcome	Data Source	Type of data	Frequency	By Whom
Antibiotic (Abx) initiation	Observation (Obs) charts/medical notes/drug charts	Time of initiation, Abx type, dose, duration	Admission/Daily	Research Nurse
Abx use (IV and Oral) in-patient	Obs charts/medical notes/drug charts	Abx type, dose, duration	Daily	Research Nurse
Abx use (IV and Oral) post discharge up to 28 days	Obs charts/medical notes/drug charts/patient report/GP record	Abx type, dose, duration	At 28 day	Research Nurse
Adverse events	Obs charts/medical notes	Date, type	Daily	Research Nurse
ICU usage	Medical notes	Date, details of admission to ICU	Daily	Research Nurse
COVID diagnosis	Medical notes	Date, clinical or laboratory confirmed	At 28 day	Research Nurse
Unscheduled readmissions	Medical notes	ICU re-admissions, re-admissions post discharge	Daily	Research Nurse
Mortality	Medical notes	Date, Description	If before Day 28	Research Nurse
Discharge	Medical notes	Date, Description	If before Day 28	Research Nurse
Serious Adverse Drug Reactions (ADRs)	Medical notes	ADR(s)	Daily	Research Nurse
Health utility	Patient reported	-	Day 28 and Day 90	EQ-5D/5L, Patient reported questionnaire, collected by

				telephone or by post
Health-related Quality of Life (EQ-5D/5L)	Patient reported	-	Day 28 and Day 90	Patient reported, collected by telephone, or by post
Resource use	Patient reported	Direct medical costs and resource use	Day 28 and Day 90	Patient reported, collected by telephone, or by post

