12.2 Lost to follow up

Data will be obtained from observation and medical notes or drug charts and will be entered into the trial database. We will ask participants who have provided deferred consent to provide contact details for members of the research team to contact them while attempting to make follow-up interviews at days 28 and 90. To minimise loss to follow up, interviews will be via telephone or electronic with both utilised where possible.

Participants will be identified as lost to follow-up if it is not possible to contact them directly for 4 weeks post day 90/hospital discharge.

13 Internal pilot and recruitment rates

We propose an internal pilot, using quantitative and qualitative data, during the first 12 months of recruitment (study months 7-16) to ensure our ability:

- to include appropriate patients,
- to implement the research process in such a way we do not delay treatment time inappropriately,
- to ensure that the results of the test are being considered and used by the treating clinicians.

The internal pilot phase will assess the site and patient absolute recruitment and consent rate, proportion of patients undergoing PCT assessments and the ability to collect the primary outcome data. Qualitative interviews with two staff per site will be conducted in order to understand how the research process and the PCT guided algorithm have integrated into their ED setting. These will be used to understand the quantitative data and provide areas for improvement in processes to enhance the efficiency of the trial.

The progression criteria have been designed to allow for mitigating strategies to be discussed to allow for some adaptation to recruitment processes. We will discuss the results with our Trial Steering Committee, before reporting to the NIHR HTA Programme, for permission to proceed. In accordance with the HTA guidance on internal pilot studies, we will exclude the first two months of recruitment from our calculation of the recruitment rate as we anticipate a 'lag phase' during which the first few sites are still being registered and participating clinicians develop confidence and competence in identifying and recruiting patients. We will constantly be assessing the criteria during the internal phase. To progress from the internal pilot to the full trial, we would be looking to utilise the following criteria in Table 2:

Table 2: Internal Pilot Criteria

Criteria (at month 9 of recruitment)	Level	Action

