18.2.1 Methods

1) Cost of illness

The cost of illness (COI) will be conducted using NHS perspective and patient's perspectives. Together these will constitute the societal perspective. It implies that data will be collected from two sources, i.e. the hospital and patients. Total costs of illness of sepsis care per patient from the ED to hospitalization will be estimated for the treatment of sepsis by multiplying the total incidences of sepsis with the unit cost of caring for a patient throughout an episode up to 28 days after discharge from hospital. In addition, the total cost of screening will be included, again both from health service and household perspective. Considering the need of care, 30 patients of each type (general ward and ICU), of 10 hospitals will be included to calculate the mean costs of illness, which will sum up a total of $30 \times 2 \times 10 = 600$ patients. Direct medical and non-medical as well as indirect costs (income loss) will be captured using a Standardbred questionnaire for patients and departmental- and patient-level costs from hospitals. By multiplying mean cost with incidence rates, the total costs will be estimated.

2) Cost saved per GBP invested in the proposed PCT intervention due to potentially avoided antibiotic prescription, avoided admissions, and other decreased resource use.

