Cost-Utility Analysis (CUA) of non-inferiority trials has been conducted elsewhere [45]. For decision making from the analysis, cost-effectiveness planes prove to be a valuable tool in the interpretation of the results in an economic equivalence or non-inferiority trial [45]. We consequently will conduct a CUA due to the expected non-inferiorly health outcomes between IA and SCA. Health outcomes (QALYs) between IA and SCA will be compared with incremental costs of intervention between the arms. To assess QALYs gained in each patient group, the EQ-5D-5L instrument will be used on each patient (or representative if the patient is not in a condition of responding) under investigation of this study at screening, the 28th day, and 90th day after randomization. All primary and secondary empirical outcomes will be compared against existing literature and systematic reviews [27, 46, 47] and other trial-based studies. If possible, a meta-analysis will be carried out. The different in costs of interventions in IA and SCA and change in health outcomes (QALYs gained) will be plotted in cost-effectiveness plane for interpreting the results of this non-inferiority trial [45].

iii) Decision-tree analysis

Using data on health outcome (QALYs) and economic outcome (Cost of intervention) and probability of correct diagnosis (including false positives and false negatives) by both procedure arms (IA and SCA) will be used for conducting probabilistic analyses based on a decision-tree using TreeAge Pros (TreeAge Company, Inc) and STATA in a probabilistic CEA. Here, patients are randomly drawn from the IA and SCA treatment arm datasets in a MonteCarlo procedure, until convergence to stable estimates. The patients may face adverse effects of treatment with antibiotics in both arms and consequently worse health status. Patients correctly treated may face different outcomes in terms of cure and health status change and related resources. All resource use, including those of complications will be related to specific costs of NHS services. Following the TreeAge pathways using transition probability distributions between health states, based on the in-trial findings and literature, costs and health utility (health status) we shall be able to estimate expected societal and health care costs and expected utility of the patients (expressed in QALYs placed in IA and SCA).

4) Cost-benefit analysis

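### Day-28 and day-90 follow-up is set up for self-report only, while the cost-utility analysis counts on a representative completing EQ-5D-5L when the patient cannot

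*Protocol*

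**What the plan says.** Participants without capacity are in the trial by design. Section 9.3 states: "If the patient lacks capacity, a consultee will be consulted as soon as possible and given information about the study". The consultee advises on participation but does not consent, and the patient's own consent is sought once capacity returns.

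The operative follow-up rules are in sections 11 and 12:

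- Section 11.1, Table 1, for EQ-5D-5L and for resource use at days 28 and 90: "Patient reported, collected by telephone, or by post".
- Section 11, on the fallback when telephone or electronic contact fails: "If unsuccessful a questionnaire booklet will be posted to the participant for them to complete and return with a pre-paid envelope".
- Section 12.2, on how follow-up contact is arranged: "We will ask participants who have provided deferred consent to provide contact details for members of the research team to contact them".
- Section 12.2, on loss to follow-up: "Participants will be identified as lost to follow-up if it is not possible to contact them directly for 4 weeks post day 90/hospital discharge".

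None of these names a proxy respondent. The health economics section does. Under cost-utility analysis, section 18.2.1 says that "the EQ-5D-5L instrument will be used on each patient (or representative if the patient is not in a condition of responding", at screening, day 28 and day 90. It says this of EQ-5D-5L only. On costs, the same section says: "It implies that data will be collected from two sources, i.e. the hospital and patients".

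**The concern.** Sites collect data from the procedures sections, not from the economics section. A participant who never regains capacity has not personally given deferred consent. Read literally, section 12.2 then provides no contact details for that person, section 11 sends the booklet to someone who cannot complete it, and the participant is counted as lost because direct contact fails. The representative's answers that section 18.2.1 expects would have no stated route into the database.

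This matters because being able to answer at day 28 or day 90 is a state reached after randomisation, is related to how ill the patient was, and could be influenced by the care under test. If the most impaired survivors are those without data, the observed EQ-5D-5L values come from a healthier subset. Any effect of the intervention on the number of impaired survivors would be partly hidden from the utility and QALY comparison and from the patient-reported part of costs. The 90-day EQ-5D-5L regression in section 17.1, Table 3 uses the same instrument and depends on the same respondent rule.

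The rule has to be settled at collection. An analysis plan can choose how to handle missing answers, but it cannot recover proxy answers that nobody asked for.

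**Working it through.** There is no figure in the plan to reproduce. The check compares the passages and then illustrates the scale.

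**Side by side**

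| Item | Sections 11, 11.1 (Table 1), 12.2 | Section 18.2.1 | Result |
|---|---|---|---|
| EQ-5D-5L respondent | Patient | Patient, or a representative if the patient cannot respond | Conflict |
| Resource-use respondent | Patient | Patients as one of two cost sources; no representative named | Omission, not a contradiction |
| Contact details | From participants who gave deferred consent | Not addressed | No stated route to a consultee |
| Loss to follow-up | Participant cannot be contacted directly | Not addressed | Does not allow for a representative |
| Hospital-side costs | Notes and charts | Hospital as one of two cost sources | Unaffected |

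Mortality comes from medical notes, and antibiotic initiation from observation charts, notes and drug charts (Table 1). Neither co-primary outcome depends on who answers a questionnaire.

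**Illustration of scale**

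Inputs from the protocol: 7,676 randomised, 5% dropout and 15% 28-day mortality (section 16.2). Input that is an assumption: the share of survivors unable to respond, taken as 5-20%, because the protocol gives none.

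- Analysable: 7,676 × 0.95 = 7,292.
- Survivors at day 28: 7,292 × 0.85 = 6,198, about 6,200.
- Without self-report: 6,198 × 0.05 = 310, to 6,198 × 0.20 = 1,240.
- As a share of those randomised: 310 / 7,676 = 4.0%, to 1,240 / 7,676 = 16.2%.

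The last line uses the number randomised because the follow-up criterion in section 13, Table 2 has that denominator. The GO level there is above 70%, so about 30 points of missing follow-up are tolerated, and this group could take about 4-16 of them.

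A lower assumption, applied to all randomised without the dropout allowance, gives 7,676 × 0.85 = 6,525 survivors. At 2%, 5% and 10% that is 130, 326 and 652 people.

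**The case against.** The strongest reply is that the protocol already provides a proxy in section 18.2.1, and that nothing gives Table 1 precedence. Patient-reported can be read as a data-source label, in contrast to medical notes. Section 11 names the participant as respondent only for the postal booklet, not for telephone or electronic contact. Contact with consultees is foreseen elsewhere: Table 2 counts consultee agreement together with patient consent, section 14 lets consultees agree to be approached for interview, and section 23.2 collects name and postcode. Lack of capacity at enrolment need not persist to day 28 or 90. Questionnaire versions and respondent fields often sit in the CRF, the Data Management Plan or the SAP.

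Much of this stands, and it limits the point. Four stronger readings that a reader might infer are not supported:

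- *Proxies are barred.* Sections 11 and 12.2 omit a proxy; they do not forbid one.
- *The contradiction extends to resource use.* Section 18.2.1 names a representative for EQ-5D-5L only.
- *These survivors drop out of the cost data.* Hospital costs, ICU use and readmissions come from records, and section 18.2 imputes missing economic data. Only the patient-reported part is exposed.
- *The loss would take 5-20 of the 30 points tolerated in Table 2.* That applies a share of survivors to a criterion based on all randomised.

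What does not stand is the conclusion that nothing needs changing. The interview route for consultees shows that such a provision can be written, and the questionnaire follow-up has no equivalent. Imputing from patients well enough to respond does not reliably represent those too impaired to do so.

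**Conclusion.** The concern holds as a conflict over who completes EQ-5D-5L and as an omission for the patient-reported part of resource use. If sections 11 and 12 are followed literally, survivors kept in the trial on consultee advice who have not regained capacity may have no data on either, and this missingness is related to severity and arises after randomisation.

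The conflict rests on the text alone. Its size is not known: the 310-1,240 people (about 4-16 points of those randomised) depend wholly on the assumed 5-20%. The protocol also gives no utility for such patients, so no bias in mean utility can be derived from it. A bias equal in both arms would cancel in the comparison; a differential one would require the number of impaired survivors, or their response, to differ by arm.

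Severity is minor to moderate, because only secondary and economic outcomes are exposed.

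**What to change.** State one respondent rule in section 11, Table 1, section 12.2 and section 18.2.1: the participant answers, or the consultee or another representative answers as proxy if the participant cannot. Apply it to both EQ-5D-5L and the resource-use questions. In addition:

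- Take the consultee's contact details when the advice is obtained.
- Count a participant as lost to follow-up only if neither the participant nor the representative can be reached.
- Record self or proxy on the CRF at each time point.
- Add a sensitivity analysis restricted to self-reports.

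The cost is a wording amendment, a proxy version of existing questionnaires and one CRF field. The small downside is that proxy answers can differ from self-reports. The CRF field and the sensitivity analysis make that visible.

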11.2 Follow-up

Day 28 and Day 90 follow-up will be via telephone or electronic, with both utilised where possible to maximise response. Patient outcomes (readmission, re-treatment, hospital-acquired infection) and use of health care resource (hospital admissions, outpatient parenteral antimicrobial therapy, other prescribed medicines, privately purchased over-the-counter medicines, GP and hospital outpatient attendance) will be captured. In addition, direct non-medical costs borne by patients/carers as a result of attending hospital (travel costs, childcare costs, expenses incurred while in hospital, self-reported lost earnings and other direct non-medical expenses) will be collected.

We will conduct semi-structured interviews with patients after the 90 days follow-up, in order to gain a detailed understanding of patients' experiences of care to aid understanding of trial results. We will encourage patients to include a close family member in the interview also. This will allow us to capture an additional perspective on the patients' care.

12 Withdrawal & lost to follow-up

12.1 Withdrawal

In this trial, the intervention used is in addition to current standard practice and poses minimal risk to the patient with the treating clinician retaining oversight on whether or not to adhere to the interventional algorithm. Due to time constraints of managing suspected sepsis

(see section 9.1), patients will be randomised into either the standard care arm or interventional arm on diagnosis with suspected sepsis, prior to consent being obtained. Participants have the right to withdraw consent for use of clinical data collected in any aspect of the trial at any time. The participants' care will not be affected at any time by declining to participate or withdrawing from the trial. Some participants may wish to withdraw the use of the data upon first approach for deferred consent, following the intervention. If a participant provides deferred consent at this stage but subsequently withdraws from the trial, clear distinction must be made as to what aspect of the trial the participant is withdrawing from. These aspects could be:

- i. Partial withdrawal from further data collection (questionnaires, clinical assessments)
- ii. Complete withdrawal from further data collection
- iii. Withdrawal of permission to use data already collected

The withdrawal of participant consent shall not affect the trial activities already carried out and the use of data collected prior to participant withdrawal.

Participants who consent and subsequently withdraw are invited to complete a withdrawal form (see Withdrawal Form in trial pack). If they decline, the withdrawal form should be completed by the researcher/clinician based on information provided by the participant. This withdrawal form should be sent to the trial manager. Any queries relating to potential withdrawal of a participant should be forwarded to the trial manager.

12.2 Lost to follow up

Data will be obtained from observation and medical notes or drug charts and will be entered into the trial database. We will ask participants who have provided deferred consent to provide contact details for members of the research team to contact them while attempting to make follow-up interviews at days 28 and 90. To minimise loss to follow up, interviews will be via telephone or electronic with both utilised where possible.

Participants will be identified as lost to follow-up if it is not possible to contact them directly for 4 weeks post day 90/hospital discharge.

13 Internal pilot and recruitment rates

We propose an internal pilot, using quantitative and qualitative data, during the first 12 months of recruitment (study months 7-16) to ensure our ability:

- to include appropriate patients,
- to implement the research process in such a way we do not delay treatment time inappropriately,
- to ensure that the results of the test are being considered and used by the treating clinicians.

The internal pilot phase will assess the site and patient absolute recruitment and consent rate, proportion of patients undergoing PCT assessments and the ability to collect the primary outcome data. Qualitative interviews with two staff per site will be conducted in order to understand how the research process and the PCT guided algorithm have integrated into their ED setting. These will be used to understand the quantitative data and provide areas for improvement in processes to enhance the efficiency of the trial.

The progression criteria have been designed to allow for mitigating strategies to be discussed to allow for some adaptation to recruitment processes. We will discuss the results with our Trial Steering Committee, before reporting to the NIHR HTA Programme, for permission to proceed. In accordance with the HTA guidance on internal pilot studies, we will exclude the first two months of recruitment from our calculation of the recruitment rate as we anticipate a 'lag phase' during which the first few sites are still being registered and participating clinicians develop confidence and competence in identifying and recruiting patients. We will constantly be assessing the criteria during the internal phase. To progress from the internal pilot to the full trial, we would be looking to utilise the following criteria in Table 2:

Table 2: Internal Pilot Criteria

Criteria (at month 9 of recruitment)	Level	Action
Number of sites open	>7 5-7 <5	GO Discuss potential mitigating strategies REVIEW/STOP
Number of enrolled participants	>2000 1000-2000 <1000	GO Discuss potential mitigating strategies REVIEW/STOP
Eligible patients randomised (defined as number randomised/number screened and on screening log*)	>50% 30-50% <30%	GO Discuss potential mitigating strategies REVIEW/STOP
Consent rate (defined as number with informed consent from patient or consultee agreement/number randomised)	>85% 50-85% <50%	GO Discuss potential mitigating strategies REVIEW/STOP
Consideration of the PCT result and algorithm during clinical decision making (defined as number algorithm adhered too /number PCT result recorded)	>50% 35-50% <35%	GO Discuss potential mitigating strategies REVIEW/STOP
Ability to collect co-primary outcome data (defined as number with complete data for both co-primary outcomes/number randomised)	>90% 70-90% <70%	GO Discuss potential mitigating strategies REVIEW/STOP
Ability to collect 28- and 90-day follow up data (defined as number with complete follow up data/number randomised)	>70% 50-70% <50%	GO Discuss potential mitigating strategies REVIEW/STOP
Reduction in the % of patients treated within time windows for usual standard care (defined as Prospective usual Standard care treatment window data/Retrospective treatment window)	<10% 10-20% >20%	GO Amend processes REVIEW/STOP
Contamination/changes to usual care in control arm	Qualitative interviews	

- Screening log will only be active during periods when a research nurse is time tabled to be in the ED/admissions unit

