6.1 Design

Parallel two-arm open-label individually randomised controlled trial with two co-primary endpoints, an internal pilot phase and group-sequential stopping rules for effectiveness and futility/safety. Participants will be randomised in a ratio of 1:1 to NEWS2 and local standard care or the PCT-guided assessment.

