9.4.2 Randomisation

Individual patients with suspected sepsis will be randomised in a 1:1 ratio to either standard clinical management (control) or standard clinical management plus PCT guided assessment (intervention). We will use minimisation with NEWS2 score and site as stratification factors and add a random element to reduce the risk of subversion. This will be implemented in a secure 24-hour web-based randomisation programme controlled centrally by the Centre for Trials Research in Cardiff.

10 Trial Intervention

PRONTO uses both the BRAHMS PCT-direct and the PathFast BRAHMS PCT. Both readers are fully validated, CE-marked point-of-care tests to determine levels of Procalcitonin in the blood. Readers for the BRAHMS PCT-Direct and all required reagents for Quality Control tests will be provided by ThermoFisher as part of a supplier agreement. The test requires 20 µl blood which will be obtained from either venous blood during standard care procedures at

triage or via a finger-prick. Recruitment using BRAHMS PCT Direct will continue until end of May 2023

From December 2022 six high recruiting sites will transition from BRAHMS PCT Direct to use the PathFast BRAHMS PCT. Readers, cartridges and associated reagents for Quality Control tests will be provided by AB Scientific as part of a separate supplier agreement. This test requires 100 µl blood which may need to be obtained as a separate venepuncture in situations where standard care phlebotomy has been completed before the PCT test is requested. These six sites will continue to recruit until the end of the study.

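### The pilot criterion for treatment delay (Protocol Table 2) is labelled a reduction but defined as its complement, and it does not say which arm it covers

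*Protocol*

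**What the plan says.** Protocol section 13 gives three aims for the internal pilot. One is "to implement the research process in such a way we do not delay treatment time inappropriately". Table 2 turns the aims into progression criteria. The row for this aim is labelled "Reduction in the % of patients treated within time windows for usual standard care" and is then "defined as Prospective usual Standard care treatment window data/Retrospective treatment window". Its levels are below 10%, 10-20% and above 20%, and the matching actions are "GO Amend processes REVIEW/STOP".

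Five other rows of Table 2 also carry a definition in brackets: eligible patients randomised, consent, use of the PCT result, co-primary data, and follow-up data. In each of them the levels apply directly to the numerator and denominator given.

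On how the criteria are used, section 13 says: "We will discuss the results with our Trial Steering Committee, before reporting to the NIHR HTA Programme, for permission to proceed". Section 6.1 sets the allocation: "Participants will be randomised in a ratio of 1:1 to NEWS2 and local standard care or the PCT-guided assessment". The lay summary (section 3.1) puts the bedside test at about 20 minutes, and section 10 says that controls do not have it.

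**The concern.** A ratio of prospective to retrospective performance falls as delay grows, whereas a reduction rises. The row attaches levels meant for a reduction to a quantity that moves the other way. Anyone who computes the row as the five other defined rows are computed gets the opposite action.

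The second difficulty is whose data enter the ratio. The wording could mean control patients only, or all participants judged against the usual-care windows. The added test happens only in the PCT arm, so the choice decides whether a delay caused by the test can be seen at all.

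This is the only row of Table 2 with a numerical level for treatment delay. The nearest other row, "Contamination/changes to usual care in control arm", is assessed by interviews and has no level. The committee and funder therefore need one clearly defined number here.

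**Working it through.** The protocol gives no computed value for this row, so there is no figure to reproduce. The check applies the printed levels to each possible reading.

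**Inputs.** Levels and definition: Table 2. Allocation 1:1: section 6.1. Let R be the retrospective and P the prospective percentage treated within the window. The protocol gives no R. The ratio P/R and the relative reduction 1 - P/R do not need it. Where an absolute difference R - P is shown, R is an assumption.

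**Step 1: direction.**

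| Change in on-time treatment | P/R as written | Action | 1 - P/R | Action |
|---|---|---|---|---|
| none | 100% | REVIEW/STOP | 0% | GO |
| 5% relative fall | 95% | REVIEW/STOP | 5% | GO |
| 15% relative fall | 85% | REVIEW/STOP | 15% | Amend |
| 25% relative fall | 75% | REVIEW/STOP | 25% | REVIEW/STOP |
| 85% relative fall | 15% | Amend | 85% | REVIEW/STOP |
| 95% relative fall | 5% | GO | 95% | REVIEW/STOP |

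GO as written needs P/R < 10%, which is a relative loss of more than 90%. Only 1 - P/R behaves as the label says.

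**Step 2: relative or absolute.** The label does not settle this, and the action can depend on it.
- Assume R = 60% and P = 51%. The relative reduction is 1 - 51/60 = 15% (Amend). The absolute reduction is 60 - 51 = 9 points (GO).
- Assume R = 80% and P = 60%. The relative reduction is 1 - 60/80 = 25% (REVIEW/STOP). The absolute reduction is 80 - 60 = 20 points (Amend).

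**Step 3: which arm.** Let d be the relative reduction in the PCT arm, with controls unchanged and the same R for both arms. With 1:1 allocation the pooled reduction is (0 + d)/2 = d/2.
- For d = 25%, the PCT arm alone gives 25% (REVIEW/STOP), pooled data give 12.5% (Amend), and control data give 0% (GO).
- Pooled data leave GO only when d/2 reaches 10%, that is d = 20%. They reach REVIEW/STOP only when d/2 exceeds 20%, that is d above 40%.
- On control data alone, no value of d is visible.

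**Step 4: why a by-arm figure needs a stated denominator.** Section 16.2 treats a fall in antibiotic initiation from 90% to 80% as success. Suppose every initiated course falls within its window and every untreated patient counts as not treated in time. Then 1 - 80/90 = 11.1%, which lands in Amend. The intended benefit would register as delay.

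**The case against.** The strongest reply is that the label fixes both the quantity and its direction, and the bracket merely names the two data sets being compared. No committee would halt a trial because timely treatment was unchanged. The action is REVIEW/STOP, it goes to the Trial Steering Committee and then the funder, and section 13 presents the criteria as guides. A reader might infer from the arithmetic that the rule stops an undelayed trial. The documents do not support that, because nothing in the row acts automatically. What stands is that the label does not supply the formula, and the table's other definitions are meant to be computed as written.

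A reader might also infer that any fall in timely treatment in the PCT arm is harm and should trigger the stop level. The documents do not support that either. The Background says the trial is meant to give clinicians more time with less severely ill patients, and the pilot aim concerns inappropriate delay. Step 4 shows how a trigger on the worse arm would penalise the planned effect. Using usual-care data to see whether research procedures disrupt care is a legitimate reading, but the row does not say that this is the one chosen.

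The larger blood sample for the second reader, which may need its own venepuncture (section 10), is not evidence here. That reader arrives from December 2022. On the timetable in sections 2 and 27 (start December 2019, pilot in months 7-16), the pilot ends around March 2021.

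This row is not the only safeguard. The data monitoring committee reviews data twice a year (section 24.4), time of antibiotic initiation is recorded (Table 1), and clinicians may overrule the algorithm (section 10.1). These soften the consequence, but none of them is a pilot progression criterion.

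**Conclusion.** The point holds as a contradiction within one progression criterion. The stated definition is the complement of a relative reduction. With the printed levels it gives REVIEW/STOP for no delay, and GO only after a loss of more than 90% of on-time treatment. This result does not depend on any assumed baseline. Since the protocol itself fixes the formula and the levels, the fault is not detail left to a later document.

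The arm is unspecified. Assuming 1:1 allocation, unchanged controls and a common retrospective rate, pooling halves a PCT-arm reduction and control-only data hide it.

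The practical risk is that those deciding on progression work from an ambiguous number. It is not that the trial would be stopped by rule.

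**What to change.** In Table 2, define the measure as 1 - (prospective % treated within the window / retrospective %), or state explicitly that it is an absolute difference in percentage points. Apply the existing 10% and 20% levels to that measure.

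Report it separately for each arm. State the denominator, so that later or withheld IV treatment intended by the algorithm is not counted as delay. No automatic trigger on the worse arm is needed, a split by NEWS2 band need not be mandatory, and the clinical time windows stay as they are.

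If the pilot decision has already been taken, state which formula and which arm or arms were used.

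The cost is a short edit to one row and a split of data already recorded. By-arm estimates will be less precise than a pooled one, and more so if enrolment at the assessment is in the 1000-2000 band of Table 2 or below it.
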